### 13.2 Secondary Time Points: 3- and 12-Months Post Randomization

The acupuncture's impact on the change of RMDQ scores at 3-months will be assessed by testing if  $\beta_{Acu} = 0$  in equation (1) since acupuncture and acupuncture plus maintenance at 3-months are the same intervention (maintenance period occurs between 3 and 6 months post randomization and neither participants in the EA condition nor the acupuncturists treating them will be aware they will receive maintenance treatments until close to the 3-month follow-up). We will follow the same general framework for 12-months as we have specified for 6-months in Section 13.1. Note that the analysis focused on the 12-month follow-up timepoint provides an important test of whether EA makes an appreciable difference over SA in sustaining or improving the effect of acupuncture on pain-related functioning that endures after the end of treatment. Finally, note that we include all times points in a single GEE model within this general modeling framework to handle correlation due to multiple outcomes on a given person. We will report both the fully saturated model 1 results and an additional final model if scenario 2 is correct for either 6 or 12 months. For example, if scenario 2 is concluded for both time points 6 and 12 months the final model is:

Scenario 2 is correct for 6 and 12 months:

$$(2) \quad E(Y_{im}|T_i, Z_i) = \alpha + \beta_{Acu}I(T_i = SA \text{ or } EA) + \beta_z Z_i + \beta_6 I(m = 6) + \beta_{12} I(m = 12) \\ + \gamma_{Acu,6} I(T_i = SA \text{ or } EA)I(m = 6) + \gamma_{Acu,12} I(T_i = SA \text{ or } EA)I(m = 12).$$

## 14. Effectiveness Analyses on Secondary Outcomes

Secondary outcomes including the PEG, patient global impression of change for pain, and physical function will be evaluated at 3-, 6-, and 12-months post randomization by comparing the measurements at the three time points to the baseline. We will follow similar framework as described above for RMDQ scores to analyze the effectiveness of acupuncture treatments, SA and EA, on the secondary outcomes. In addition, the occurrence of an  $\geq 30\%$  improvement in RMDQ and PEG measures at 3-, 6-, and 12-months compared to the baseline will be evaluated under the same framework. A link function will be chosen appropriately for each outcome.

## **15. Additional Effectiveness Analyses for Primary Outcome**

### **15.1 Moderators**

The five potential effect moderators including sex (male and female), age group (65-74, 75-84, 85+), race/ethnicity (non-Hispanic white and other), patient expectation (measured with PRO, see Section 4), and RMDQ at baseline (<18, 18+) will be evaluated by investigating their impact on acupuncture's effectiveness on RMDQ score change at 6-months (primary time point) compared to the baseline outcome. We will follow the proposed framework in Section 13.1 with additional interaction terms between individual moderators, intervention, and indicator of 6=months in model (1) and (2). The moderators will be assessed separately. For the race and ethnicity moderator we will further adjust for a spline of calendar time to account for potential calendar time confounding due to over-sampling certain racial and ethnic subgroups to increase numbers to improve representation. For the knots in the spline we will use the times when we changed the sampling proportions of racial groups across the study. Other clinically meaningful moderators, for example cognitive impairment, frail elderly, co-morbid pain conditions, co-morbid depression, will be considered given there is greater than 10% of participants in the sample for a given subgroup of interest. All moderator analyses that are conducted will be reported in a single manuscript. Interpretation of findings therefore will be in context of number of tests being conducted and are only exploratory findings.

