participant's current pain condition (presence of sciatica), potential prognostic risk for pain-related impairment (e.g., pain catastrophizing, fear avoidance, treatment expectations, and disability/workers compensation), and pain-related service use (e.g., back surgery, injections, opioid and other common prescription medications, various types of exercise, psychological counseling, and use of acupuncture) align with RTF recommendations or are specific to the study's focus on acupuncture. We will measure patient expectations of acupuncture using one item from the EXPECT short form⁶² and using the term acupuncture as the therapy. The question uses a 0 to 10 scale focused on expectations related to acupuncture treatment for chronic low back pain. We will include questions about the impact of the COVID-19 pandemic on the ability to get health care and on their overall health (physical, emotional, and mental, including pain). These were adapted from a patient questionnaire developed by the Pain Management Collaboratory funded by the NIH – Department of Defense and Veterans Administration⁶³. We will ask several questions from the FRAIL scale to characterize participant frailty at the time of enrollment in this study. Finally, we will also collect data from the EHR on other co-morbidities, including various pain conditions. This will allow us to describe the population as well as conduct some moderator analyses.

Aim 1 measures (Baseline AND 3, 6 and 12-monthfollow-up).

Back-related disability will be measured with the 24-item Roland-Morris Disability Questionnaire (RMDQ),⁶⁴ which asked whether 24 specific activities were limited due to back pain during the past week (yes or no). This legacy measure has been found to be reliable, valid and sensitive to clinical changes.⁶⁵⁻⁶⁹ It is appropriate for telephone administration for patients with moderate disability.⁷⁰ The RMDQ will be our primary outcome measure and will be measured as a continuous variable. The minimal clinically important difference (MCID) for the RMDQ in our population is 2 points⁷¹ or 30% improvement from baseline.⁷² The MCID will be examined in a secondary analysis.

As a secondary outcome measure and a HEAL CDE, we will use the PEG scale (a validated, 3-item pain-intensity and pain-related interference composite measure assessing Pain intensity, as well as pain interference with Enjoyment of Life and General Activity).⁷⁵

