We will conduct a set of prespecified moderator analyses using a similar analysis as Aim 1 except include interactions with the moderator and treatment groups. Moderators of interest include age (65-74; 75-84; 85+), patient expectations and gender. However, we do not anticipate being powered to detect a difference in treatment effects between men and women. According to results from the Acupuncture Trialists Collaboration, gender has not been consistently found to be related to benefits from acupuncture.¹⁰⁵ We will look at race and ethnicity as well, but we will not be powered to detect a difference between groups. We have identified potentially important clinical conditions that may well diminish treatment effect (i.e., cognitive impairment, frail elderly, co-morbid pain conditions, co-morbid depression). If these are sufficiently common in our study participants, we will perform pre-specified moderator analyses.

We will also conduct exploratory per protocol analyses assessing dose response to see if the effect changes dependent upon number of acupuncture treatments received and include UMC as having 0 treatments in the analyses. We will flexibly model the trajectory of the primary outcome at 3 months by number of treatments to see if there is a threshold effect of treatment dose. Further we will run adherence analyses comparing amongst those who adhered in the 3-months of standard acupuncture (at least 8 treatments and last visit indicated by acupuncturist that they completed treatment or at least 12 treatments) compared to UMC and amongst those adhered to those who did not adhere within the acupuncture groups. We will do a second set of adherence analyses but define adhered as only those that the acupuncturist indicated as completing treatment. Since these analyses are not intent-to-treat we will include further potential confounders that are associated with being non-adherent or receiving differential number of treatments.

Aim 2: We will perform economic evaluations from both the payer (Medicare) and health care sector perspectives alongside the randomized pragmatic trial comparing usual medical care (UMC) to the addition of 3-months of acupuncture (SA) and 3-months of acupuncture and 3-

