## 2. Study Outcomes

### 2.1 Primary Outcome in Effectiveness Analyses

Primary Outcome	Brief Description of Measure	Outcome Measured By	Time Frame
Change in back-related disability at 6-month post randomization (continuous)	Change in back-related disability is defined as score change in RMDQ, a 24-item questionnaire which asked whether 24 specific activities were limited due to back pain during the past week.	Patient reported outcome (PRO) of scores from RMDQ at baseline and 6-month	Baseline to 6-month

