### 3. Additional Variables for Effectiveness Analyses (Moderators and Predictors)

The following predictors/covariates and/or **moderators** will be assessed related to the **primary outcome**. Note: variables pre-specified for baseline adjustment in all models include: baseline outcome value, age, sex, race, and healthcare system

Moderators & Predictors	Definition	Role	Data Source
Sex	Male vs. Female/Other Sex at birth as reported by subject; assessed using HEAL CDE Demographic question	Moderator/Predictor	Patient self-report at baseline
Age	65-74, 75-84, 85+	Moderator/Predictor	EHR
Race/Ethnicity	White, non-white	Moderator/Predictor	Patient self-report at baseline
Expectations of acupuncture	EXPECT 1-item question – categorical based on the distribution of responses	Moderator/Predictor	Patient self-report at baseline
RMDQ	<18, 18+	Moderator/Predictor	Patient self-report at baseline
Pain catastrophizing	6-item subscale required by HEAL CDE	Predictor/covariate	Patient self-report at baseline

Moderators & Predictors	Definition	Role	Data Source
Fear avoidance	NIH Task Force single item	Predictor/covariate	Patient self-report at baseline
Frailty	Frailty Index 	Predictor/covariate	Patient self-report at baseline and EHR data
Medical morbidity	Carey Ambulatory-based Morbidity Score 	Predictor/covariate	EHR data; based on last 12 months
Multiple non-malignant musculoskeletal pain conditions	1 pain cluster vs. >1 > 1 pain-related ICD-10 diagnosis corresponding to more than one (>1) of the non-malignant musculoskeletal chronic pain condition clusters developed for the National Pain Strategy chronic pain condition clusters  Back pain Neck pain Limb/extremity pain, joint pain and arthritic disorders Fibromyalgia Headache Orofacial, ear, and temporomandibular disorder pain Musculoskeletal chest pain General pain subcategory of the Other painful conditions cluster	Predictor/covariate	EHR data; diagnoses in participant's EHR extracted at baseline for prior 360 days
Mental health mood disorders	ICD-10 diagnosis for depression and/or anxiety diagnosis	Predictor/Covariate	EHR data; diagnoses in subject's EHR extracted at baseline for prior 360 days

Moderators & Predictors	Definition	Role	Data Source
COVID19 pandemic impact	Two questions modified from assessments designed by Pain Collaboratory. These focus on impacts of ability to get health care and on overall health	Time-varying covariate	Patient self-report

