## 13. Effectiveness Analyses on Changes in RMDQ Scores

We will evaluate the effectiveness of acupuncture and acupuncture plus maintenance relative to Usual Medical Care (UMC) at 3-, 6- (primary time-point), and 12-months after randomization. We will conduct a longitudinal analysis including the continuous outcome, change in Roland Morris Disability Questionnaire (RMDQ) from baseline (primary outcome) measured at all follow-up times, in one model estimated using generalized estimating equations (GEE).  We will use a working independence correlation matrix and will calculate standard errors using the robust sandwich estimator to account for within-person and within-in provider (some participants may see the same provider) correlation. All models will adjust for baseline RMDQ score, age, sex, race and HCS. Further, if missing RMDQ at 6 months (primary time point) is more than 15% in any study arm, or differential by more than 10% between any two arms, we will use imputation approaches as the primary analysis to account for missing data and further adjust for any baseline variables that are predictive of loss to follow-up determined as described in Section 9. All analyses will be conducted following an intent-to-treat approach, including all individuals randomized regardless of their engagement with, or exposure, to the intervention.

We will include interactions between intervention groups and time (3-, 6-, and 12-months) to estimate time-specific intervention effects. Time will be included as a categorical variable. To gain power, since acupuncture and acupuncture plus maintenance at 3-months are the same intervention (maintenance period occurs between 3 and 6 months post randomization and neither participants in the EA condition nor the acupuncturists treating them will be aware they will receive maintenance treatments until close to the 3-month follow-up), we will combine acupuncture groups at 3-month follow-up. We chose GEE as our analytic method because our primary outcome, RMDQ, is not expected to be normally distributed. From our experience working with RMDQ data, adjusting for baseline RMDQ value results in more normally distributed residuals. However, we didn't want to make that assumption a priori and therefore chose GEE.

Our specific model for change in RMDQ is the following:

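### Baseline RMDQ and expectation are tested as moderators only in categories, which costs power for a roughly linear interaction and leaves the expectation groups undefined

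*SAP*

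**What the plan says.** **Baseline RMDQ.** SAP 15.1 gives the moderator as "RMDQ at baseline (<18, 18" and above), and the table in SAP Section 3 repeats the two groups. Neither place explains the choice of 18. SAP 2.1 describes the RMDQ as "a 24-item questionnaire which asked whether 24 specific activities were limited due to back pain during the past week", so the score runs from 0 to 24.

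**Expectation.** Protocol 6.2.2 (Baseline Interview) says of the single item: "The question uses a 0 to 10 scale focused on expectations related to acupuncture treatment for chronic low back pain". SAP Section 3 will make it "categorical based on the distribution of responses", with no number of groups and no cut rule. SAP 15.1 refers the reader to Section 4 for this measure, but Section 4 covers sample size and the definition is in Section 3. Protocol 9.6 gives cut-points for age but none for expectation: "Moderators of interest include age (65-74; 75-84; 85+), patient expectations and gender".

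**Model and status.** SAP 15.1 adds "additional interaction terms between individual moderators, intervention, and indicator of 6=months in model (1) and (2"), one moderator at a time. It says the results "are only exploratory findings" and that every moderator analysis conducted will appear in a single manuscript. Baseline RMDQ is also a covariate in the main analysis (SAP 13): "All models will adjust for baseline RMDQ score, age, sex, race and HCS". The score is therefore kept for adjustment and grouped only when it acts as a moderator.

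**The concern.** Both moderators are numeric and collected at baseline. Grouping a score for an interaction test treats everyone within a group as alike. If the treatment effect changes gradually with the score, much of the evidence for that change is lost. The loss is greatest when the cut is far from the centre of the distribution, and 18 is three-quarters of the way up the scale.

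For expectation there is a second matter. With no stated number of groups and no rule, several groupings would be consistent with the SAP, and the analyst must choose among them.

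What is at stake is the interpretation of a null moderator result. Protocol section 3 wants the subgroup analyses to show who benefits and who does not. A null interaction based on a small 18+ group could be read as no effect modification when the test had little chance of finding any. SAP 15.1 will consider other clinical moderators only if the subgroup exceeds 10% of the sample, but it applies no such check to RMDQ 18+.

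**Working it through.** **The plan's own figures.** The documents state no power for any moderator analysis. The main-comparison figures reproduce. With 210 evaluable per arm, a 2-point difference and SD 6, unadjusted pairwise power is 92.7%. Under Fisher's LSD (40,000 simulated trials) it is 91.0% to 91.1% when both acupuncture arms improve, and 91.1% to 91.3% when only EA does. 210/0.8 = 262.5, which rounds up to 263 per arm.

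**Inputs for the moderator check.** From the documents: scale 0-24, cut at 18, and 210 evaluable per arm. Assumed: baseline mean 10 to 16 and SD 5 to 6. The SDs in SAP Section 4 (6 for planning, 5.42 at 6 months, 5.11 for change) are not baseline values.

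**Efficiency.** For a linear interaction, the share of information kept by a cut is the squared correlation between the cut variable and the full score. For a normal score this is φ(c)²/[p(1−p)], with c = (17.5 − mean)/SD and p the share at 18+.

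- Mean 10, SD 5: c = 1.50, φ = 0.1295, p = 0.0668, giving 0.0168/0.0623 = 0.27.
- Mean 14, SD 6: c = 0.583, φ = 0.3365, p = 0.280, giving 0.1132/0.2015 = 0.56.

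The RMDQ is bounded and whole-numbered, so the table uses a normal distribution discretised to 0-24 (mean and SD are those before truncation). Power after the cut, starting from 80% on the full score, is Φ[(1.960 + 0.842)·√eff − 1.960]. The sample-size multiple is 1/eff.

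| Mean, SD | At 18+ | Per arm of 210 | Efficiency | Power | Multiple |
|---|---|---|---|---|---|
| 10, 5 | 7% | 14 | 0.28 | 32% | 3.6 |
| 12, 6 | 17% | 35 | 0.45 | 47% | 2.2 |
| 14, 6 | 25% | 53 | 0.53 | 53% | 1.9 |
| 16, 5 | 35% | 74 | 0.60 | 59% | 1.7 |

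Over this range even the best single cut-point reaches only 0.66 to 0.68.

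**Simulation.** 4,000 trials had 210 UMC and 420 acupuncture patients, baseline mean 12 and SD 6 (5.38 after truncation), residual SD 6, and adjustment for the continuous baseline score. The standard error of the interaction slope is (6/5.38)·√(1/210 + 1/420) = 0.094, so a slope of 2.80 × 0.094 = 0.26 points per RMDQ point gives 80% power. Simulated power was 80% with the score and 46% with the cut. With no interaction, the rejection rates were 5.7% and 4.7%, so the cut does not inflate type I error.

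**Expectation.** For a normal score in equal-sized groups, the share kept is the sum over groups of [φ(lower) − φ(upper)]²/p. This gives 0.64 for a median split, 0.79 for tertiles and 0.86 for quartiles. An 11-point item may not divide into equal groups, so these are guides only.

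**The case against.** The strongest case against has four parts.

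**The RMDQ cut is fixed in advance.** This stands. A reader might infer that the data set the groups for both moderators, or that groups are picked by looking at outcomes. The documents support neither. The value 18 appears in two places in the SAP. The expectation groups are to follow the responses to a baseline item. Protocol 6.2.3 and SAP Section 7 keep outcome data from the study biostatisticians during the trial, and Protocol 6.2.3 keeps treatment assignment out of datasets until lock. What remains open is the unstated number of expectation groups, the rule for them, and when they will be set.

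**The efficiency figures presume a linear interaction.** This also stands. Because the measure is a squared correlation it works both ways: if the true modification is a step at 18, a linear test loses the same share. SAP 13 does not expect the RMDQ to be normally distributed, and patients with low baseline scores have little room to improve, so linearity should not be taken for granted. The SAP does not, however, argue for a step at 18.

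**Categories have real uses.** They need no linearity assumption and give subgroup effects that are easy to read. This is a reason to keep them for display, but not to make them the only test.

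**The consequence is small.** The findings are exploratory and all will be reported together. This limits the weight of the point. It does not explain why a score already used for adjustment should be cut for the interaction.

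**Conclusion.** The point holds as a cheap improvement. Testing baseline RMDQ only at 18 keeps about 28% to 60% of the information on a linear interaction (27% at the low end by the plain normal formula), which is equivalent to needing about 1.7 to 3.6 times as many patients. The range rests on an assumed baseline mean of 10 to 16 and SD of 5 to 6, which the documents do not give, and on a roughly linear interaction. The loss for expectation is smaller, about 14% to 36% for two to four equal-sized groups, and it cannot be pinned down until the grouping is stated.

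Only the expectation grouping is open to analyst choice. A reader might go further and conclude that these moderator tests have excess false positives or that the main result is weakened. Neither follows: the fixed RMDQ cut leaves type I error at about 5%, and the primary analysis does not use these groups.

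**What to change.** In SAP Section 3 and SAP 15.1, make the interaction test for baseline RMDQ and for expectation use the continuous score. Use a linear term as the test, and a restricted cubic spline with knots stated in advance to check curvature. Keep <18/18+ and the expectation categories for displaying subgroup estimates, with the expectation cut-points written down before unblinding. Correct the cross-reference in SAP 15.1 so that expectation points to Section 3.

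The cost is SAP wording. No new data are needed, and the SAP already uses similar tools: a calendar-time spline in 15.1 and flexible modelling of treatment number in 15.2. There are two downsides. The linear test loses power if the true modification is a step at 18, and the spline check adds degrees of freedom, more so with three arms.

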### **15.2 Dosage of Acupuncture Treatment and Adherence**

We will flexibly model the change of the primary outcome at 3 months by number of treatments to see if there is a threshold effect of treatment dose. Further we will run adherence analyses comparing amongst those who adhered in the 3-months of SA (at least 8 treatments and last visit indicated by acupuncturist that they completed treatment or at least 12 treatments) compared to UMC and amongst those adhered to those who did not adhere within the SA groups. A second set of adherence analyses will be carried out with an alternative definition of adherence as only those who the acupuncturist indicated as completing treatment. Since these analyses are not intent-to-treat, we will include further potential confounders which are potential predictors for being non-adherent or receiving differential number of treatments.

## **16. Exploratory Effectiveness Analyses on Tertiary Outcomes at 3-, 6-, and 12-Months**

We will assess the tertiary outcomes including PROMIS measures of ability to engage in social roles, anxiety, depression, fatigue, and sleep disturbance/duration in exploratory analyses. These measures are related to other common complaints which acupuncture treatment may have impact on, so improvements on these metrics after acupuncture treatment will be expected. However, since there are less data linking them to acupuncture, especially in a chronic pain population, we will conduct only exploratory analyses on these outcomes. We will fit models for these outcomes separately similar to the model for secondary outcomes at 3-, 6-, and 12-months as described in Section 15 and observe the estimated effects of acupuncture treatments.

